7.3. Site Poolability

Although data for this study will be collected from multiple site, no site pooling analyses are planned.

7.4. Handling of Missing, Unused, and Spurious Data and Dropouts

Every effort will be undertaken to minimize missing data. In time-to-event outcomes drop-outs will be censored at the time of discontinuation, consistent with the Kaplan-Meier approach.

Missing (accidentally, due to withdrawal, missing follow-up or loss to follow-up, etc.), unused and spurious data will remain identifiable in the database. Data from subjects that cannot be analyzed for a specific variable will be displayed as missing in the relevant summary tables. In this manner, all data for a specific variable are accounted for. Unless otherwise specified, no statistical techniques will be used to impute missing data. The number of subjects included in each analysis will be reported so that the reader can assess the potential impact of missing data.

In the case of partial dates, if only the month and year are known, the event or assessment will be analyzed as if it occurred on the 15th of that month. If only the year is known, the event or assessment will be analyzed as if it occurred on June 30th of that year. These resolutions of partial dates are subject to the restrictions that events must occur no earlier than the procedure date.

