## 10.2. Reporting of Adverse Events

### 10.2.1. Evaluation and Documentation of Adverse Events and Device Deficiencies

Investigators are required to evaluate and document in the subject's medical records all adverse events (AE) and device deficiencies (per the definitions in Table 5) observed in study subjects from the time they are enrolled until they are exited from the study. All AE should be followed through their resolution or until subject's study exit.

All AEs that occur during the study need to be reported to Medtronic via the AE eCRF. Documented pre-existing conditions are not considered to be reportable unless there is a change in the nature or severity of the condition. Pre-existing events should be reported as AE in the situation where a new treatment has to be started or an existing treatment has to be changed to treat the adverse event and the event is accompanied with signs and symptoms. In addition, after the subject has completed his/her two-year follow-up visit, only SAEs and device-related AEs need to be reported to Medtronic.

Unavoidable events are conditions which do not fulfill the definition of an Adverse Event, meaning those medical occurrences, clinical signs (including abnormal laboratory findings), diseases or injuries that are not untoward in nature; specifically, those resulting from the intended injury such as the index TAVR procedure. The events listed in Table 6 are expected for patients undergoing TAVR, and do not need to be reported as AE, unless they occur outside of the stated timeframe, are otherwise considered to be an AE according to the treating investigator, or are suspected or confirmed to be device-related.

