**Table 6. Non-reportable medical occurrences associated with the index implant procedure**

Event	Timeframe (hours) from the Index Procedure
Short transient episode of arrhythmia (including ventricular fibrillation) during index procedure	0
Confusion, anxiety and/or disorientation (other than TIA/stroke) starting within 48 hours with or without medical intervention	120 (5 days)
Temporary change in mental status (other than TIA/stroke) not requiring additional medical interventions or new medical assessments (eg, CT)	72
Dizziness and/or lightheadedness with or without treatment	24
Headache with or without treatment	72
Sleep problems or insomnia with or without treatment	120 (5 days)
Mild dyspnea or cough with or without treatment	72
Oxygen supply after extubation/“forced breathing therapy”	48
Diarrhea with or without treatment	48
Obstipation/Constipation with or without treatment	72
Anesthesia-related nausea and/or vomiting with or without treatment	24
Low-grade fever (<101.3°F or <38.5°C) without confirmed infection	48
Low body temperature	6
Pain (eg, back, shoulder) related to laying on the procedure table with or without treatment	72
Incisional pain (pain at access site) with or without standard treatment and patient not returning to clinic to have additional treatment	No time limit
Pain in throat and/or trachea due to intubation	72
Mild to moderate bruising or ecchymosis	168 (7 days)
Atelectasis/Pleural Effusion not requiring punctuation	168 (7 days)
Edema resulting in weight increase up to 4 kg/9lbs from baseline	168 (7 days)

For all observed AEs, investigators should assess and document the following information on the Adverse Event eCRF:

- Date of onset or first observation
- Date of site’s first awareness
- AE code number
- Description of the event
- Seriousness of the event
- Causal relationship of the event to the TAV or surgical valve
- Causal relationship of the event to the DCS and/or LS

- Causal relationship of the event to the TAVR implant procedure
- Treatment required
- Outcome or status of the event
- Date of resolution
- For all deaths, investigators should assess and document the following information on the Adverse Event eCRF
  - Date of death
  - Primary death category
  - Causal relationship of the event to the TAV or surgical valve
  - Causal relationship of the event to the DCS and/or LS
  - Causal relationship of the event to the implant procedure

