7.2. General Methodology

Descriptive statistics will be used to report study data. For continuous variables (eg. age), the mean, median, standard deviation, minimum, maximum and interquartile ranges (IQR) will be presented. For categorical variables, the number and percentage of subjects in the category of interest will be presented.

For time to event variables, Kaplan-Meier analyses of event rates at 30 days, 1 year and annually through end of study will be presented. For these analyses, the time points will correspond to 30 days, 365 days, 730 days, 1095 days, 1460 days, 1825 days, 2190 days, 2555 days, 2920 days, 3285 days and 3650 days post implantation respectively. At each time point with data, the product limit estimate of the event, the number of subjects at risk, the number of subjects with events, and the 95% confidence interval will be presented. For subjects without an event, the date of censoring will be the latest date of all follow-up visits, assessments, and events (including death).

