7.9. Evaluation of Objectives

7.9.1. Primary Safety Endpoint

All-cause Mortality or Disabling Stroke Rate at 30 days.

Hypothesis/Decision criteria:

No specific hypotheses or pass/fail criteria have been set. The analysis will be descriptive and no statistical hypothesis test will be performed.

Endpoint Definition/Parameters to Be Estimated:

The endpoint is the KM event rate of all-cause mortality or disabling stroke at 30 days post procedure.

Data Collection and Analysis Method:

Data will be collected on event case report form. Death and stroke events will be adjudicated by the CEC. CEC adjudicated all-cause mortality or disabling stroke will be used in the analysis.

Analysis Dataset:

This objective will be analyzed for all attempted implant set.

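### The partial-date rule in SAP 7.4 is bounded only by the procedure date, so it can date an event before a documented event-free visit or after the subject's death.

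*SAP*

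**What the plan says.** SAP 7.4 (Handling of Missing, Unused, and Spurious Data and Dropouts) has two substitution rules. With month and year known, the event or assessment "will be analyzed as if it occurred on the 15th of that month". For the other case: "If only the year is known, the event or assessment will be analyzed as if it occurred on June 30th of that year". One limit follows: "These resolutions of partial dates are subject to the restrictions that events must occur no earlier than the procedure date". Neither document gives an upper limit, or a lower limit at the last contact at which the subject was known to be alive or event-free. Protocol 12.8 (Missing Data) has no partial-date rule. SAP 7.2 fixes a censoring date only for subjects who have no event, so it cannot correct an event that has been misdated.

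These dates decide what is counted. SAP 7.9.1 states: "The endpoint is the KM event rate of all-cause mortality or disabling stroke at 30 days post procedure". SAP 7.9.2 fails device success for a death within 30 days. SAP 7.2 and 7.9.3 use the same event times for Kaplan-Meier estimates at annual landmarks to 3650 days.

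The data for tighter limits are already collected. The adverse event eCRF items listed after Table 6 in Protocol 10.2.1 include "Date of onset or first observation", the date of the site's first awareness and the date of death. Visit dates are also on file.

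**The concern.** An imputation rule should fill a gap without overriding what is known. This one ignores known dates on both sides. A subject examined and found event-free can be given an event dated before that visit, and a subject who has died can be given a stroke dated after death. In the first case the error can carry an event across day 30 into the primary safety endpoint, or across an annual landmark. The primary results are meant for a regulatory submission and rest on few events (SAP Table 2 illustrates four in 150), so one misdated event is visible. If the conflict is found only at analysis, someone must decide ad hoc, knowing the outcome, which date to use.

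**Working it through.** **Inputs.** Substitution dates and the procedure-date limit: SAP 7.4. Endpoint at day 30: SAP 7.9.1. Visit windows of days 30 to 45 and 365 to 395: SAP section 5. N = 150 and the illustrative event counts: SAP Table 2. All examples use non-leap years.

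**The plan's own figures.** Clopper-Pearson 95% limits for 4/150 are 0.73% to 6.69%, and for 142/150 are 89.76% to 97.67%. Both match Table 2 (0.7%, 6.7%; 89.8%, 97.7%). The partial-date rule has no stated figure of its own.

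**The rule applied to specific cases.**

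1. *Month only, across day 30.* Procedure 14 February; event-free visit 17 March (day 31); stroke later in March, day unknown. Imputed date 15 March = day 29. It counts in the 30-day rate although the true event is after day 31.
2. *Year only, across day 30.* Procedure 10 June; event-free visit 15 July (day 35); event later that year, only the year known. Imputed date 30 June = day 20. It counts in the 30-day rate.
3. *Year only, across the 1-year landmark.* Procedure 1 September; seen alive 15 September of the next year (365 + 14 = day 379); dies later that calendar year, only the year known. Imputed date 30 June = 273 days to 1 June + 29 = day 302. The death counts in 1-year mortality although the subject was alive at day 379.
4. *After death.* Procedure 1 March; death 11 March (day 10); stroke in March, day unknown. Imputed date 15 March = day 14, four days after death.

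**Largest possible error.** Year only: 30 June to 31 December = 184 days too early; 1 January to 30 June = 180 days too late. Month only: the 15th to the 31st = 16 days too early; the 1st to the 15th = 14 days too late.

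**Effect of one event.** 1/150 = 0.67 points. The illustrative 4/150 = 2.7% (0.7% to 6.7%) becomes 3/150 = 2.0% (0.4% to 5.7%) or 5/150 = 3.3% (1.1% to 7.6%), by exact limits.

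**How often a date crosses day 30, given that it is partial.** All 365 procedure dates were enumerated, with true event days uniform. A substitution falling before the procedure was set to the procedure date. Both are assumptions.

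| Date known to | True day | Moved to the wrong side of day 30 |
|---|---|---|
| Month | 0 to 30 | 1,260/11,315 = 11.1% moved out |
| Month | 31 to 60 | 1,523/10,950 = 13.9% moved in |
| Month | 31 to 45 | 1,516/5,475 = 27.7% moved in |
| Year | 0 to 30 | 45.2% moved out |
| Year | 31 to 60 | 46.4% moved in |

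The enumeration uses no visit, death or awareness dates. These shares therefore measure the fixed mid-month and mid-year conventions, not the missing limits. Limits would reduce them but not remove them. For example, a procedure on 10 June with a true event on 5 July (day 25) is imputed to 15 July (day 35), and only an awareness, death or exit date before 11 July (day 31) would bring it back.

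**How often a year-only date precedes the last event-free contact.** Suppose that contact and event fall in the same year, both uniform, with the event after the contact. The imputed date precedes the contact when the contact falls after 30 June, which has probability (184/365)² = 0.254.

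**The case against.** The strongest reply is that partial dates will seldom arise where they matter most. The onset field also accepts the date of first observation. Serious events are due to the sponsor within 72 hours of site awareness (Protocol Table 7). Deaths and strokes are adjudicated by the CEC from source documents, and disabling status needs a 90-day mRS (Protocol Appendix V). Case 1 requires an adjudicated disabling stroke, within two weeks of a clinic visit, whose day nobody recorded. The analysis is descriptive, with no pass/fail criterion. All of this stands, and it limits the weight of the point, but it does not make the rule right in the cases where it is used.

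Case 4 cannot change the 30-day composite, because the death already counts. In the all-stroke curve it matters only if the stroke crosses a landmark. That also stands.

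Three stronger readings are tempting but unsupported.

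- *The rule misplaces 11% to 14% of events around day 30.* Those shares are conditional on a date being known only to the month, and the documents give no rate of such dates. They come from the mid-month convention.
- *A year-only event is dated before the last event-free contact about half the time.* That overlooks that the contact must precede the event. With that condition the share is about 25% under uniform timing.
- *Pre-procedure events become day-0 events.* Protocol 10.2.1 does collect adverse events "observed in study subjects from the time they are enrolled until they are exited from the study", and enrollment is at consent. But the SAP does not say how its restriction is applied, and SAP 7.2 counts Kaplan-Meier times from implantation. The restriction can be read as governing post-procedure events only. The wording should be made explicit; a reclassification of events is not established.

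**Conclusion.** The point holds as a defect in a stated rule. SAP 7.4 can date an event before a visit at which the subject was documented alive or event-free, including moving an event from after day 30 into the primary safety endpoint, and can date an event after death. Per affected event, the effect on the 30-day rate is 0.67 points at N = 150. The total effect cannot be given because the expected number of partial dates is not stated. It is assumed to be near zero for the first 30 days and larger in late follow-up, where the year 6, 8 and 9 contacts may be by telephone. The practical weight therefore lies with year-only dates (error up to 184 days) and the annual landmarks. Table 2 is unaffected. The change is worth making because it is cheap and removes direct contradictions with recorded data.

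**What to change.** Add to SAP 7.4:

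- After substitution, an imputed date is moved, if necessary, into an interval. Lower limit: the later of the procedure date and the last contact at which the subject was documented alive (for death) or event-free (for other events). Upper limit: the earliest of death, study exit, data cut and the site's first-awareness date.
- The procedure-date limit applies only to events not recorded as pre-procedure.
- All primary-endpoint events with a partial date are listed. Where the bounded interval spans day 30, the 30-day rate is also shown with the earliest and with the latest possible date. This shows the remaining uncertainty; counting every such event as within 30 days would be a debatable worst-case choice.

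Cost: a few sentences in the SAP and a few lines of code, with no new data. There is one small downside: an event present but unrecognised at a contact recorded as event-free may be dated slightly late.

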7.5. Adjustments for Multiple Comparisons

No multiple comparisons/multiplicity adjustments will be made.

7.6. Demographic and Other Baseline Characteristics

Baseline demographic and clinical variables will be summarized for as attempted implant analysis set. All continuous variables will be summarized with means, medians, standard deviations, minimums, maximums, and interquartile ranges. Categorical variables will be summarized with frequencies and percentages.

7.7. Treatment Characteristics

Procedure data will be summarized for the attempted implant analysis set. Continuous variables will be summarized with means, medians, standard deviations, minimums, maximums, and interquartile ranges. Categorical variables will be summarized with frequencies and percentages.

7.8. Interim Analyses

No interim analyses will be conducted for this observational study.

7.9. Evaluation of Objectives

7.9.1. Primary Safety Endpoint

All-cause Mortality or Disabling Stroke Rate at 30 days.

Hypothesis/Decision criteria:

No specific hypotheses or pass/fail criteria have been set. The analysis will be descriptive and no statistical hypothesis test will be performed.

Endpoint Definition/Parameters to Be Estimated:

The endpoint is the KM event rate of all-cause mortality or disabling stroke at 30 days post procedure.

Data Collection and Analysis Method:

Data will be collected on event case report form. Death and stroke events will be adjudicated by the CEC. CEC adjudicated all-cause mortality or disabling stroke will be used in the analysis.

Analysis Dataset:

This objective will be analyzed for all attempted implant set.

7.9.2. Primary Efficacy Endpoint

Device Success Rate.

Hypothesis/Decision criteria:

No specific hypotheses or pass/fail criteria have been set. The analysis will be descriptive and no statistical hypothesis test will be performed.

Endpoint Definition/Parameters to Be Estimated:

Device success, defined as composite endpoint:

- Absence of procedural mortality, AND
- Correct positioning of a single prosthetic heart valve into the proper anatomical location, AND
- Absence of moderate or severe total prosthetic valve regurgitation (at 18 hours to 7 days)

Data Collection and Analysis Method:

The components of device success will be determined as follows:

- No death event occurs within 30 days post-procedure, or on or before the discharge date (if the discharge date is longer than 30 days post-procedure);
- In the procedure CRF, the answer to "Correct positioning of the prosthetic heart valve into proper anatomical location" and "only 1 TAV implanted" should be both "YES";

The criteria for ECHO will be based on the ECHO Core Lab Data for the time interval of 18 hours to 7 days:

- Absence of moderate or severe prosthetic valve regurgitation. Total Aortic Prosthetic Regurgitation on the ECHO CORE LAB form equals to none, trace, mild, or mild to moderate.

All of the above components must be satisfied to count as a device success. If any of the above components fails, the endpoint will be counted as a failure.

For the overall device success rate, the numerator will be the number of subjects whose procedures result in device success as described above, and the denominator will be the number of subjects whose device success results are not missing. Note that this analysis excludes those subjects with a missing response to any of the above three components (eg, the field "Post-implant Severity of Total Aortic Regurgitation" = "Unable to Assess" or "Not Recorded") and without a "NO" response to any of the components. In addition to the device success rate, the 95% C.I. will also be provided.

Analysis Dataset:

This objective will be analyzed for the implanted analysis set.

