## 8.6. TAVR Implant Procedure

The implantation procedure is performed according to the standard procedures of the implanting physicians. In countries where required, including the United States, the local heart team's interventional cardiologist(s) and cardiac surgeon(s) must jointly participate in the intra-operative technical aspects of the TAVR procedure. Procedural aspects specific to the Medtronic TAVR system should be performed according to the Instructions for Use. The following variables will be collected regarding the TAVR implantation procedure:

- Name of the primary and secondary operator
- Anesthesia type (general or local)
- Delivery catheter access site and vessel diameter of access site
- Use of EnVeo InLine Sheath alone, OR use of separate introducer sheath size and type
- Pre-deployment BAV (yes/no)
- Use of rapid pacing during BAV and deployment (yes/no)
- Size of TAV implanted
- Post-implant dilation (yes/no)
- Post-implant pressures at final result (LV systolic and end-diastolic, aortic systolic and diastolic)
- Implantation of TAV within the desired location (yes/no)
- Post-implant degree of prosthetic regurgitation by angiography (Sellers criteria, 45)
- Post-implant degree of prosthetic paravalvular regurgitation by TEE, if performed
- Post-implant degree of prosthetic transvalvular regurgitation by TEE, if performed
- More than one TAV implanted (yes/no)
- Patency of coronary arteries post-implant (yes/no)
- Estimated contrast volume used
- Total procedural time(minutes): time in procedure room to exit from procedure room
- Information on use of resheath/recapture feature (Definitions of resheath/recapture use are provided in Appendix IV)
- Occurrence of adverse events
- If TAV implantation not attempted, reason why

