Note: Repeat procedures are reported on the appropriate eCRF (Surgical Intervention or Catheter Reintervention)

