## 2.0 Other Related Complications (continued)

Complication	Definition
Conversion to open surgery	Conversion to open sternotomy during the TAVR procedure secondary to any procedure-related complications
Unplanned use of cardiopulmonary bypass	Unplanned use of CPB for hemodynamic support at any time during the TAVI procedure
Coronary artery obstruction	Angiographic or echocardiographic evidence of a new, partial or complete, obstruction of a coronary ostium, either by the TAV prosthesis itself, the native leaflets, calcifications, or dissection, occurring during or after the TAVR procedure.
Ventricular septal perforation	Angiographic or echocardiographic evidence of a new septal perforation during or after the TAVR procedure
Mitral valve apparatus damage or dysfunction	Angiographic or echocardiographic evidence of new damage (chordae, papillary muscle, or leaflet) to the mitral valve apparatus or dysfunction (eg, restrictions due to the TAV of the mitral valve during or after the TAVR procedure
Cardiac tamponade	Evidence of new pericardial effusion associated with hemodynamic instability and clearly related to the TAVI procedure
Prosthetic valve thrombosis	Any thrombus attached to or near an implanted valve that occludes part of the blood flow path, interferes with valve function, or is sufficiently large to warrant treatment. Valve-associated thrombus identified at autopsy in a patient whose cause of death was not valve related should not be reported as valve thrombosis.
Valve migration	After initial correct positioning, any observed movement (upward or downward) of the TAV within the aortic annulus from its initial position, with or without consequences.
Valve embolization	The TAV moves during or after deployment such that it loses contact within the aortic annulus
Ectopic valve deployment	Permanent deployment of the TAV in a location other than the aortic root
TAV in TAV deployment	Additional valve prosthesis is implanted within a previously implanted TAV because of sub-optimal device position and/or function, during or after the index procedure.
Hemolysis	Red cell destruction confirmed by lab data Minor hemolysis: No intervention required Major hemolysis: Requires intervention (eg, iron supplements, transfusion, invasive intervention).

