This is a multi-center, prospective, single-arm clinical study designed to evaluate procedural efficacy and safety results at 30 days.

Study methods include the following measures to minimize potential sources of bias:

- An external, independent Clinical Events Committee (CEC) will review and adjudicate, at minimum, all deaths and endpoint-related adverse events. Safety endpoint results will be based on CEC adjudications.

- All sites will follow a standardized protocol for acquisition of echocardiographic endpoint data.
- An Echocardiography Core Laboratory will evaluate all echocardiograms; echocardiographic endpoint results will be based on Core Lab assessments.
- Study sites should follow their institutional procedures for maintenance of imaging and laboratory equipment used for assessing the study variables.

Subjects will be followed up for 10 years. The enrollment period is estimated to be between 12-24 months therefore the estimated total duration of the study (first subject enrolled to last subject completing his/her last follow-up exam) is estimated to be 12 years.

The population includes males and females with severe aortic stenosis with a clinical indication for surgical aortic valve replacement with a bioprosthesis who are at low predicted risk of mortality at 30 days for surgical aortic valve replacement and have bicuspid aortic valve anatomy.

The point of enrollment is when written informed consent is obtained from the subject.

All follow-up periods are defined as the number of days after the date of the index procedure (first attempted procedure). The index procedure = Day 0.

Baseline	Within 12 weeks prior to submitting to the screening committee (except for MDCT and coronary arteriography as noted in CIP Section 3.3.9)
Discharge	Discharge from index procedure or 7 days post implant, whichever comes first
30 Days	Between 30 and 45 days post implant
1 Year	Between 365 and 395 days post implant
2 Year	Between 730 and 760 days post-implant
3 – 10 Years	Between implant anniversary date and +/-60 days after

6. Determination of Sample Size

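### Device success can miss a second valve, embolization, or replacement or explant of the valve occurring between the index procedure and the qualifying echo

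*SAP*

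**What the plan says.** SAP 7.9.2 defines device success by three components and gives each a source.

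- **Procedural mortality:** no death within 30 days, or by discharge if that is later.
- **Position and single valve:** the SAP begins "In the procedure CRF, the answer to" and names two items, "Correct positioning of the prosthetic heart valve into proper anatomical location" and "only 1 TAV implanted". Both must be YES. No time window is given.
- **Regurgitation:** the core-lab grade of total regurgitation at 18 hours to 7 days must be no worse than mild to moderate.

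Any failed component makes the subject a failure. A subject with a missing component and no NO on any other is left out of the denominator. The analysis uses the implanted set.

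Protocol 8.6 lists the matching position and valve-count variables among the data collected about the implantation procedure. Later events are recorded elsewhere. A note in Protocol Appendix V, section 2.0, says "Repeat procedures are reported on the appropriate eCRF (Surgical Intervention or Catheter Reintervention"). The same section defines embolization as possible after deployment, and TAV-in-TAV as "Additional valve prosthesis is implanted within a previously implanted TAV because of sub-optimal device position and/or function, during or after the index procedure". The Event Code List gives embolization code 158 and TAV-in-TAV code 160. SAP 7.9.2 uses neither these codes nor the reintervention forms.

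**The concern.** The second component closes with the procedure form, but the third is read up to a week later. A corrective intervention in between is invisible to the second component and improves the third, because the echo grades the valve as it stands after the rescue. If the valve has been removed and there is no qualifying echo, the subject leaves the denominator instead of counting against the device.

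Both routes push the primary efficacy rate upward. The study has no hypothesis and no pass/fail criterion, so the rate and its interval are the result. Protocol 5.2 names positioning difficulty and implantation of multiple devices among the possible consequences of bicuspid anatomy, so the gap falls on a question the study was set up to answer. Protocol 12.1 also says the results will be compared with the TAVR arm of the randomized Low Risk Trial. If such events are more frequent in bicuspid valves, using the form-only rule in both cohorts would not cancel the error.

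**Working it through.** **1. Test the written rule on a case.** Take a subject with both procedure-form items YES, a second valve placed on day 2, a core-lab echo on day 5 showing mild regurgitation, and no death by day 30.

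- Death component: met.
- Position and single-valve component: met, because the form describes the index procedure and the day-2 valve is reported on another eCRF.
- Regurgitation component: met, on the rescued result.
- Outcome under SAP 7.9.2: success, with two valves implanted.

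Now take a subject with both items YES, the valve explanted on day 2, alive at day 30 and no qualifying echo. No component is NO and one is missing, so the subject is excluded.

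**2. Reproduce the plan's figures.** From SAP Table 1, pooled device success is (367 + 272 + 57 + 57) / (385 + 291 + 59 + 60) = 753/795 = 94.7%. Applied to 150 subjects this gives 142. The exact (Clopper-Pearson) 95% limits for x successes in n are:

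- lower = Beta quantile 0.025 with parameters x, n − x + 1
- upper = Beta quantile 0.975 with parameters x + 1, n − x

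For 142/150 these are 89.8% and 97.7%, matching SAP Table 2. No figure in the plan is wrong; the problem lies in the derivation rule.

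**3. Size of misclassified successes.** Let k be the number of planned successes that should be failures. The documents give no value for k, so 0 to 3 is an assumption. The rate is (142 − k)/150:

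- k = 0: 142/150 = 94.7% (89.8% to 97.7%)
- k = 1: 141/150 = 94.0% (88.9% to 97.2%)
- k = 2: 140/150 = 93.3% (88.1% to 96.8%)
- k = 3: 139/150 = 92.7% (87.3% to 96.3%)

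Each case is worth 1/150 = 0.67 points. The actual denominator is implanted subjects with a non-missing result. It may be below 150, and the weight per case is then slightly larger.

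**4. Size of dropped failures.** If one of the eight planned failures (150 − 142) is excluded as missing, the reported rate is 142/149 = 95.3% against 142/150 = 94.7%, about 0.6 points too high.

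**5. How likely is at least one case?** With an assumed per-subject rate r of such events that otherwise pass, the expected count is 150r and P(at least one) = 1 − (1 − r)^150:

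- r = 0.2%: 0.3 expected, probability 26%
- r = 0.5%: 0.75 expected, probability 53%
- r = 1%: 1.5 expected, probability 78%
- r = 2%: 3 expected, probability 95%

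These rates are illustrations only.

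**The case against.** The strongest reply is that the rule is coherent as it stands. The 18-hour-to-7-day window is attached to regurgitation only, and the objective is procedural safety and efficacy. Position and valve count may therefore be meant as end-of-procedure facts. A reader might infer that the definition demands a single, well-placed valve through day 7; the documents do not say so. This part of the objection stands. It does not close the gap, because even on that reading an echo taken after a rescue does not grade the result of the index procedure.

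Other points that stand:

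- **Index-procedure events are captured.** Ectopic deployment, or a second valve or embolization during the index procedure, should already produce a NO on the form. It would be wrong to say that the rule misses positioning failures in general.
- **Some later events still fail,** through death within 30 days or moderate or severe regurgitation on the core-lab echo.
- **Migration is a poor trigger.** Appendix V defines it as movement after initial correct positioning, whether or not it has consequences. Failing every code 157 would penalise trivial movement. Counting any reintervention is also too broad, since the listed repeat procedures include balloon valvuloplasty and a plug for paravalvular leak.
- **The form is site-reported.** It is tempting to say that operators grade their own work, but the SAP names only the procedure CRF, and Protocol 8.13.1 has authorized site personnel complete eCRFs. The statement that "Safety endpoint results will be based on CEC adjudications" concerns safety endpoints and does not reach this component.
- **The events are not hidden.** SAP 7.9.3 reports valve dysfunction requiring a repeat procedure from 30 days onward. It does not enter device success.
- **Comparability matters.** The documents do not show how the historical studies or the Low Risk TAVR arm derived this component. A stricter rule applied here alone could create an artificial deficit.

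Protocol 8.13.1 also requires eCRFs to reflect the latest observations. That general duty does not tell sites to change an index-procedure answer after a later event, and Appendix V directs repeat procedures to other forms.

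**Conclusion.** The concern holds for post-procedure events before the qualifying echo: a second valve, embolization, or surgical replacement or explant of the valve. For these, SAP 7.9.2 as written can credit a rescued result as a success or remove the subject from the denominator.

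The size is unknown and may be zero. Under the assumption of 0 to 3 misclassified successes in 150, the planned 94.7% becomes 94.7% to 92.7%, and the exact lower limit moves from 89.8% to between 89.8% and 87.3%. The documents do not support reading this as a demonstrated bias of a known amount. No decision rule changes, because none is set. It is still worth correcting, since the estimate will support regulatory submissions and the remedy uses data already collected.

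**What to change.** In SAP 7.9.2:

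1. State that the position and single-valve component runs from the index procedure to the qualifying echo, and at most to day 7.
2. Keep the two form items, and also count device success as failed if valve embolization (158), TAV-in-TAV (160), a second valve, or surgical replacement or explant of the TAV is recorded in that interval.
3. Apply this even when the echo is missing. The existing rule already keeps a subject with a NO on any component as a failure, so this fits its structure.
4. Do not fail migration (157) on its own. Count it only when it leads to one of the events in item 2.
5. Apply the same derivation to the Low Risk TAVR arm where its data allow, and also report the rate under the form-only rule now in the SAP, so that a like-for-like figure remains available.

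No special instruction on which echo to use is needed for these subjects, because they already count as failures. The cost is SAP wording and a merge of the adverse event and reintervention eCRFs with the procedure form. The reported rate may be slightly lower.
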